#### 2.2.2 Human Experience with Elevated Urate

#### A) Epidemiology of Urate and Disease (other than PD)

Higher Serum Urate: Clinical Consequences and Associations – The planned intervention, oral inosine titrated to moderate elevation of serum urate levels is expected to increase risks of gout and uric acid kidney stones, which are caused by local increases in urate or uric acid concentration. As discussed below, the risk of uric acid urolithiasis can be markedly reduced by avoiding or raising low urinary pH, whereas the risk of gout can be minimized but not eliminated by avoiding prolonged elevation of serum urate concentrations above ~8 mg/dL (the upper limit of the target range). In contrast, there is no conclusive evidence that increasing serum urate will affect the risk of cardiovascular events or other diseases. Nevertheless, we will preemptively exclude from the trial individuals at high cardiovascular risk and will closely monitor the subjects for any evidence of harm. Most importantly, we expect that the hypothesized slowing of PD progression produced by urate elevation will more than compensate for the known adverse effects of higher urate levels, which are reversible or treatable.

#### 1) Epidemiology of Urate and Gout

Although it is widely accepted that high levels of serum urate predispose to gout, there are few published prospective epidemiologic studies that have investigated the relationship between prior urate levels and the risk of incident gout.

As part of the Framingham Study, a total of 5,127 individuals were examined biennially for a follow-up of 12 years. The incidence of gout increased with increasing levels of urate. Over this period, gout developed in 18 (1.1%) of 1,615 men with urate < 6 mg/dL; 26 (7.3%) of 354 men

with urate between 6 and 6.9 mg/dL, and 11 (14.2%) of 78 men with urate between 7.0 and 7.9 mg/dL. The corresponding annual incidence rates were thus approximately 0.1%, 0.6%, and 1.1%. The incidence rate of gout increased sharply at urate levels above 8 mg/dL, with 8 (36%) of 22 men in this range developing gout. In women, gout developed in 3 (0.1%) of 2,405 with urate < 6 mg/dL; 5 (7.0%) of those with urate between 6.0 and 6.9 mg/dL; and 3 (27.2%) of those with urate between 7.0 and 7.9 mg/dL. The corresponding annual incidence rates were thus approximately 0.01%, 0.6%, and 2.6%. Only one woman had a serum urate level above 8 mg/dL and she did not develop gout.

In a study of 2,046 initially healthy men in the Normative Aging Study followed for about 15 years there were 87 incident cases of gout. The annual incidence of gout was 4.9% in men with serum urate values of 9.0 mg/dL or more, compared with an annual incidence of 0.5% for serum urate levels of 7.0 to 8.9 mg/dL, and an annual incidence of only 0.1 % for serum urate levels < 7.0 mg/dL. St Among men with serum urate levels ranging between 7.0 and < 8.0 mg/dL (the target interval in SURE-PD3), the annual incidence of gout was 0.4% in the Normative Aging Study.

In a Chinese prospective study among men with hyperuricemia (defined as serum concentrations > 7.0 mg/dL at baseline) 42 cases of incident gout were documented during the 5-year follow-up. 86 Annual incidence rates of gout in this study were 2.2% for serum urate levels of 7.0-7.9 mg/dL, 5.5% for 8.0-8.9 mg/dL, and 12.2% for > 9.0 mg/dL.

Thus, the associated risk of gout might be considered an acceptable risk if the benefits of increasing urate by administration of inosine can be demonstrated to delay the progression of PD. Based on available epidemiological evidence, one may expect an excess of 0.3 to 2.6 episodes of gout for 100 persons per year in the group targeted to 7.0-8.0 mg/dL of serum urate. However, there was no episode of gout or gout-like symptoms among PD patients with over 25,000 subject-days of exposure to urate-elevating inosine in our phase 2 trial, and similarly none were reported among ~200 MS patients in multiple prior trials of urate-elevating inosine (despite numerous kidney stone AEs among these subjects). Also of note, inosine is unlikely to cause gout per se, as inosine-induced hyperuricemia is expected to be reversible and gout is defined as a disease of recurrent episodes of urate crystal-induced arthritis and its degenerative consequences.

## 2) Epidemiology of Urate and Renal Lithiasis

Formation of uric acid stones. Higher urate generation leads not only to higher urate levels in the serum, but also in the urine (uricosuria) and consequently the risk of kidney stones, specifically those comprising uric acid crystals. However the main determinant of uric acid stone formation is not uricosuria, but an acidic urinary pH.  Uric acid stone formation can thus be prevented even in individuals with high urine urate, provided their urinary pH is greater than 5.5.  Although cases of nephrolithiasis were reported in some of the previous trials using inosine (see above), no monitoring of urinary pH was implemented in any of those studies. Our strategy for preventing uric acid nephrolithiasis in SURE-PD3 includes exclusion of subjects with acidic urine, monitoring of urinary pH,  and raising of urinary pH by administration of potassium citrate or other alkalinization therapy if it falls below 5.5 (or 6.0 in the presence of uric acid crystalluria).  In the past, concerns were raised that uricosuria could also contribute to the formation of calcium oxalate stones,  but this relationship was not supported by the results of further study.

## 3) Correlations between Serum Urate and Hypertension

A positive association between baseline serum urate and risk of developing hypertension has been consistently observed in numerous longitudinal studies, and seems to be independent from other known risk factors.  In recent studies in which relative risk estimates were adjusted for baseline body mass index, blood pressure, and other potential confounding factors, the increased risk of

hypertension seems to be linear, without obvious threshold effects. The relative risk associated with a 1.0 mg/dL difference in serum urate concentrations ranged from 1.09 (95% CI: 1.02 to 1.17) among 3,073 men followed for six years as part of the Multiple Risk Factors Intervention Trial (MRFIT) to 1.31 among 2,520 individuals (men and women) followed for 10 years as part of the Beaver Dam Study; the pooled relative risk was 1.13 (95% CI: 1.06 to 1.20) in a 2011 meta-analysis. Results of the same meta-analysis suggested that the association between urate and hypertension tends to be stronger at younger ages and in women. An increase in blood pressure has also been found among individuals who did not develop hypertension during the follow-up. For example, a 1.0 mg/dL increase in serum urate concentration was found to be associated with a 2.5 mm Hg increase in systolic blood pressure (SBP) and a 1.2 mm Hg increase in diastolic blood pressure (DBP) after 5-years of follow-up in the Beaver Dam Study, whereas a smaller average increase was reported over a one year period in the MRFIT (0.33/0.16 mm Hg, SBP/DBP).

However, recent studies in humans with MS and PD (see below) on the effects of urate-elevating inosine found no detectable effect on blood pressure (SBP, DBP or their orthostatic changes) of inosine that elevated serum urate by up to 4 mg/dL to achieve chronic stable levels of 7-8 mg/dL. Thus any increase in blood pressure attributable to urate elevation that might be observed in SURE-PD3 would likely be modest. Further, among individuals with PD, blood pressure tends to decline early in the disease course. Nevertheless, blood pressure will be closely monitored during the trial and anti-hypertensive treatment will be initiated or adjusted as needed.

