#### **Diagram of Timeline & Treatment**

#### **Interventions, Evaluations and Duration**

Capsules containing 500 mg of inosine (active drug) or lactose (placebo) will be taken orally up to two capsules three times per day (i.e., up to 3 gm/day) for 24 months. In the inosine-treated group the number of capsules taken per day will be titrated to serum urate levels – measured at trough at all study visits (V's in the above diagram) no more than three months apart – in order to achieve concentrations of 7.1-8.0 mg/dL. Initial dosing will be tailored to individualized factors including gender and pretreatment serum urate, and then advanced gradually toward the projected target dose. Adjustments in dosing of placebo capsules in the control arm will be algorithm-based to match dosing of inosine capsules in the active drug arm.

Following study drug discontinuation all subjects will be followed during a 3-month wash-out period (w/o) by telephone calls (T's in the above diagram) and a final study visit. All study visits after screening will include measurement of the primary outcome variable (MDS-UPDRS) and most will include secondary outcome variables: adverse events, dose adjustments, disability warranting initiation of dopaminergic therapy, Quality of Life in Neurological Disorders (Neuro-QOL), 39-item Parkinson's Disease Questionnaire (PDQ-39), Schwab & England Activities of Daily Living (S&E ADL) scale, Montreal Cognitive Assessment (MoCA), and orthostatic vital signs.

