In spite of these limitations, an adverse effect of urate on cardiovascular events cannot be excluded. Because many large investigations did not find a significant association, such effects would most likely be modest. The actual number of events attributable to the intervention would depend not only on the relative risk, but also on the underlying incidence of cardiovascular events in the study population. For example, if inosine treatment increased the risk of major cardiovascular events (including nonfatal stroke, nonfatal myocardial infarction, or death from any cardiovascular cause) by 20%, the number of expected cases attributable to the treatment would be 1.5 per 1,000 persons per year in a population with a baseline rate of 7.7 per 1,000, the rate based on 2,607 events observed during the 20-year follow-up of nearly 18,000 men aged 40 to 84 at baseline in the Physician Health Study. 129

It should be emphasized again that there is no convincing evidence that elevating serum urate will increase the risk of cardiovascular events. The number of excess cases provided as an example above is thus hypothetical. However, to try to further minimize risk, individuals with a history of major cardiovascular morbidity or decreased kidney function will be excluded from SURE-PD3, and all subjects will be closely monitored for increases in blood pressure and other early signs of coronary or cerebrovascular events.

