# 3.2.4.3 Reducing Risk of Possible Cardiovascular Adverse Effects

Also of particular relevance to the PD population is the risk of cardiovascular disease (CVD), which is an important even if uncertain risk of higher urate levels, as detailed above. Individuals with higher serum urate have a significantly increased risk of hypertension, coronary heart disease, and stroke. Although these associations may in part be confounded by obesity and other risk factors, 98,105 potential for a long-term neuroprotective effect of urate or its precursors must be weighed against potential adverse cardiovascular effects. It is worth noting that amongst PD patients in developed countries CVD is common and indeed is a leading cause of death. Moreover, CVD and its major sequelae of myocardial and cerebral infarction are far less reversible than urate-related crystal disease. On the other hand, recent data from a small study of urate-elevating inosine in MS and from the SURE-PD trial showed no evidence of blood pressure elevation compared to placebo despite months to years of substantial elevation of serum urate levels.

The main approach to reducing possible CVD risk during the SURE-PD trial was through the exclusion of those with a significant history (Sec. 4.2), particularly prior myocardial infarction or stroke and heart failure with an ejection fraction <45%. The lack of evidence for inosine-associated CVD events in the SURE-PD trial reflects a sample size and follow-up period that are too small to offer substantial reassurance. Accordingly, these exclusion criteria will remain unaltered in the phase 3 trial. Assessments for development of CVD during the trial will include frequent review of all AEs, and regular blood pressure and electrocardiographic monitoring.

Although serum urate has also been linked to metabolic syndrome and diabetes,  which is itself a major risk factor for CVD, SURE-PD data  showed no effect of long-term urate-elevating inosine treatment on body weight or blood sugar. In any event, risk of type II diabetes-related CVD will also be reduced through exclusion of those with evidence of CVD.

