## 6.1.2 Vital Signs, their Orthostatic Changes, Weight and Height

Blood pressure (supine and standing), heart rate (supine and standing), and body weight will be measured at Screening Visit 2, Baseline Visit, Week 12, Month 12, Month 24 and Month 27. Height will be measured at the Baseline Visit only.

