#### **6.1.7** Adverse Events

Adverse events (AEs) will be documented at each study visit, starting with the signing of informed consent. Events that occur prior to administration of first dose of study drug will be noted accordingly. Information on adverse effects of study medication and on intercurrent events will be determined at each visit by direct questioning of the subjects, review of concomitant medications, and vital sign results.

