## 10.5.7 Safety and Tolerability Outcomes

Overall AE and SAE rates will be compared between treatment groups by negative binomial regression. Time to first SAE will be compared between treatment groups by Kaplan-Meier logrank test. The proportion of subjects experiencing (a) each type of AE, classified by MedDRA preferred term and system organ class, (b) clinically-significant abnormal labs, and (c) clinically significant abnormal vital signs, including orthostatic hypotension defined as positional dizziness or other clinical symptoms of orthostatic hypotension or a drop in systolic and diastolic blood pressures of 20 mm Hg and 10 mg Hg or more, respectively, when moving from a supine to a standing position will be compared between treatment groups by Fisher's exact test.

Assuming no administrative censoring, all subjects will be classifiable as tolerant or intolerant, with subjects lost to follow-up or withdrawing consent classified as intolerant. Tolerability will then be estimated by simple proportions tolerant at 12 weeks and 24 months. Serum urate elevation will be declared tolerable at each time point if its exact one-sided lower 95% confidence bound is greater than 50%. If evaluation of tolerance is censored, then Kaplan-Meier product-limit estimates and their complementary log-log confidence bounds will be used. We will explore the relationship between tolerance and use of dopaminergic therapy using Cox regression with use of dopaminergic therapy as a time-dependent covariate.

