3.3 Safety Outcomes

Safety of oral inosine titrated to achieve trough serum urate in the range 7.1 to 8.0 mg/dL will be evaluated by comparing active vs. placebo treatment groups with respect to overall adverse event (AE) and serious adverse event (SAE) rate, time to first SAE, and proportions of subjects experiencing (a) each type of AE, classified by Medical Dictionary for Regulatory Activities (MedDRA) preferred term and system organ class, (b) clinically-significant abnormal labs, and (c) clinically significant abnormal vital signs, including orthostatic hypotension defined as positional dizziness or other clinical symptoms of orthostatic hypotension or a drop in systolic

and diastolic blood pressures of 20 mm Hg and 10 mg Hg or more, respectively, when moving from a supine to a standing position.

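### Change in supine and standing blood pressure, a named safety endpoint, is only described by arm, while weight and ECG are tested in mixed models; add it to the same model and report a confidence interval.

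*Protocol*

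**What the plan says.** **The commitment.** Protocol 2.2.2 A) 3) reviews the association between urate and hypertension and concludes that "blood pressure will be closely monitored during the trial and anti-hypertensive treatment will be initiated or adjusted as needed". Protocol 2.2.2 A) 4) repeats this as cardiovascular mitigation: "all subjects will be closely monitored for increases in blood pressure and other early signs of coronary or cerebrovascular events". Protocol 6.1.7 says that information on adverse effects "will be determined at each visit by direct questioning of the subjects, review of concomitant medications, and vital sign results".

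**The schedule.** Under Protocol 6.1.2, supine and standing blood pressure, heart rate and "body weight will be measured at Screening Visit 2, Baseline Visit, Week 12, Month 12, Month 24 and Month 27". The visit lists in Protocol 7.2 and the schedules in Protocol 7.7 and SAP 2.8 agree. Readings at unscheduled visits are at the investigator's discretion (Protocol 7.5.1); a reading is required at the visit that ends in-person follow-up (Protocol 7.5.2).

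**The analysis.** One bullet of SAP 4.5 makes change from baseline in supine and standing pressure, heart rate, orthostasis and body weight a safety endpoint. SAP 6.7.3 then gives descriptive statistics for vital signs at each visit by arm, and no comparison. SAP 6.7.4 describes weight and ECG parameters and also tests them by arm in linear mixed models. The supine-to-standing difference and orthostatic hypotension are secondary efficacy endpoints and are modelled by arm (SAP 4.3 and 6.6.3). The SAP governs matters of data analysis (SAP 1).

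**The concern.** Blood pressure is one of the few possible harms that the protocol answers with a specific promise of close monitoring, because the intervention deliberately raises urate. It shares an endpoint bullet with body weight, yet weight receives a model-based comparison and pressure does not. The safety question is whether mean pressure rises on inosine and by how much. That calls for an arm difference with an interval, and the plan does not specify one.

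The monitoring text raises a smaller, separate issue. A reader of Protocol 2.2.2 and 6.1.7 would expect pressure readings to inform review at each visit. At seven of the ten on-treatment visits none is scheduled, although participants attend and give blood.

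**Working it through.** **1. Visit count.** Protocol 3.1 places on-treatment clinic visits at Weeks 3, 6 and 12 and Months 6, 9, 12, 15, 18, 21 and 24, which is ten (V01 to V10). Pressure is scheduled at V03, V06 and V10: 3 of 10. It is not scheduled at V01, V02, V04, V05, V07, V08 or V09. Serum urate is drawn at all ten.

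**2. Gaps.** The readings fall on days 0, 84, 360 and 720, so the gaps are 84, 360 − 84 = 276 and 720 − 360 = 360 days. With readings at all ten visits the longest gap would be 180 − 84 = 96 days.

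For scale, assume that onset is equally likely on any of the 720 days and is found only at the next scheduled reading. The mean wait is the sum of squared gaps divided by (2 × 720):
- as scheduled: (84² + 276² + 360²)/1440 = 212,832/1440 = 148 days;
- all ten visits (gaps 21, 21, 42, 96, then six of 90): 60,462/1440 = 42 days.

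Questioning at visits, unscheduled readings and outside care would shorten both figures.

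**3. What the orthostatic models can see.** They analyse standing minus supine pressure. If treatment raises both by d, then (standing + d) − (supine + d) = standing − supine. A rise common to both positions cancels, so these models cannot detect it.

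**4. Precision of the missing estimate.** For a difference in mean change at one visit with n per arm, the 95% half-width is 1.96 × SD × √(2/n). The documents give no SD for blood pressure change, so 10 to 20 mm Hg is an assumption. The 135 per arm is half of the planned 270.
- n = 135: SD 10 gives 2.4, SD 15 gives 3.6 and SD 20 gives 4.8 mm Hg.
- n = 60 (assumed, for a late visit after early closeout), SD 20: 1.96 × 20 × √(2/60) = 7.2 mm Hg.

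These are simple two-mean figures. They take no account of repeated measures.

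**5. A scale for reading those half-widths.** Protocol 10.3.1 expects an average urate rise of 3 mg/dL. Protocol 2.2.2 A) 3) cites observational rises per 1 mg/dL of 0.33/0.16 mm Hg over one year in one cohort and 2.5/1.2 mm Hg after five years in another. Multiplied by 3, these are about 1.0/0.5 and 7.5/3.6 mm Hg. The scaling assumes causality and linearity, and neither figure is a 24-month prediction. An effect near 1 mm Hg could not be resolved at any half-width above.

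**The case against.** **Description is the SAP's usual safety convention.** Adverse events (SAP 6.7.1) and all safety laboratory values (SAP 6.7.2) are also summarised without a test; weight and ECG are the exception. This stands: pressure has not been singled out for weaker treatment. It does not explain why weight, in the same endpoint bullet, is modelled and the variable promised close monitoring is not.

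**A reader could compute an interval.** SAP 6.7.3 gives means and SDs by arm and SAP 6.1.2 adds the number of subjects, so a crude interval per visit can be derived. This also stands, and it narrows the gap. The crude version treats each visit separately and does not use the other visits to handle missing readings.

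**Other comparisons exist.** Under Protocol 10.5.7, the proportion with clinically significant abnormal vital signs "will be compared between treatment groups by Fisher's exact test". SAP 3.3 keeps the outcome as "clinically significant abnormal vital signs, including orthostatic hypotension defined as positional dizziness or other clinical symptoms of orthostatic hypotension". The word including does not limit the category to falls in pressure. However, a fall is the only abnormality defined, SAP 6.7 carries no test for this outcome, and a proportion does not estimate mean change. Hypertension could also appear among the tabulated adverse events.

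**Risk is expected to be small.** Protocol 2.2.2 A) 3) reports no detectable pressure effect in earlier inosine studies and expects any rise to be modest. Protocol 3.2.4.3 makes exclusion of cardiovascular history the main safeguard. This stands and limits the importance of the point.

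**Close monitoring is unquantified.** No section promises a reading at every visit, and the operative sections agree with each other. Protocol 6.1.7 can be read as covering vital signs where they are taken. That leaves loose wording rather than a broken rule.

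A reader might go further and infer that Protocol 3.2.4.3, which promises "frequent review of all AEs, and regular blood pressure and electrocardiographic monitoring", contradicts the schedule. It does not: the sentence applies the same adjective to ECG, which is taken on treatment only at Months 12 and 24. Nor does the synopsis show a defect specific to blood pressure. Its phrase "All study visits after screening will include measurement of the primary outcome variable (MDS-UPDRS) and most will include secondary outcome variables" introduces a pooled list in which MoCA, PDQ-39 and Schwab & England follow the same sparse visits as orthostatic vital signs (BL, V03, V06, V10 and SV).

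**Conclusion.** The point holds as a modest analysis improvement. A named safety endpoint that the protocol stresses has only descriptive analysis in the governing SAP. A model of a type already planned for weight and ECG would supply the missing arm difference and interval. The expected precision rests on an assumed SD and on how many participants remain at each visit.

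The schedule mismatch is secondary and concerns the design as written: 3 of 10 visits, with gaps of 276 and 360 days. The 148-day and 42-day waits rest on the assumptions stated with them and are not tied to any clinical outcome.

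Two stronger conclusions are tempting and unsupported. One is that participants were harmed or left unmonitored: adverse-event questioning and medication review run at every visit, and a sustained rise would still show at V03, V06 and V10. The other is that the trial could firmly exclude a 7.5 mm Hg rise. That relies on something like 135 per arm with nobody missing. At a half-width of 7.2 mm Hg, the estimate itself would have to be about 0.3 mm Hg or lower (7.5 − 7.2), and SAP 4.6 and 4.8 record early closeout.

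**What to change.** **Main change (SAP 6.7.4).** Add supine and standing systolic and diastolic pressure to the linear mixed model for weight and ECG, in the safety and tolerability sample. Report the arm difference in change from baseline with a 95% confidence interval at V03, V06 and V10, show SV separately as off treatment, and give the number contributing at each visit. The readings are already collected at BL, V03, V06, V10 and SV, so the cost is one more use of an existing model and a few table rows.

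**Secondary change, for the design as written.** Either add a cuff reading in Protocol 6.1.2 and the schedule at the seven on-treatment visits that lack one, at a few minutes per visit already attended, or reword Protocol 2.2.2 A) 3), 2.2.2 A) 4) and 6.1.7 to match 6.1.2. Sites had been told of early closeout by the time of this SAP, so for this trial the main change is the useful one.

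**Optional reporting detail.** A by-arm count of antihypertensive starts or increases, and a stated threshold for raised pressure, would help a reader but are not needed for the point.
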